**Table 3: Analysis populations**

Population	Description
Enrolled	All participants who signed the ICF
Full Analysis Set (FAS)	All participants who were randomized in the study. This analysis set will be used for the efficacy analyses.
Scalp Special Site Analysis Set (SSSAS)	All participants who were randomized in the study within scalp special site involvement at baseline. This analysis set will be used for the efficacy analyses for the scalp special site.
Genital Special Site Analysis Set (GSSAS)	All participants who were randomized in the study within genital special site involvement at baseline. This analysis set will be used for the efficacy analyses for the genital special site.
Intertriginous Special Site Analysis Set (ISSAS)	All participants who were randomized in the study within intertriginous special site involvement at baseline. This analysis set will be used for the efficacy analyses for the intertriginous special site.
Facial Special Site Analysis Set (FSSAS)	All participants who were randomized in the study within facial special site involvement at baseline. This analysis set will be used for the efficacy analyses for the face special site.
Safety Analysis Set (SAS)	All participants who received at least 1 (complete or partial) administration of study intervention (i.e., the treated population).
Immunogenicity Analysis Set (IAS)	All participants who received at least 1 (complete or partial) administration of guselkumab and who had at least 1 sample obtained after their first administration of guselkumab
PK Analysis Set (PKAS)	All participants who received at least 1 complete administration of guselkumab and had at least 1 valid blood sample drawn for PK analysis
PD Analysis Set (PDAS)	All participants who received at least 1 (complete or partial) administration of study intervention

ICF = informed consent form; PD = pharmacodynamics; PK = pharmacokinetics

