
Table 6: Analysis Sets

Analysis Sets	Description
	
ointment or foam, tacrolimus, pimecrolimus, anthralin/dithranol, coal tar preparations, PDE4 inhibitors, e.g., crisaborole, or other topicals used for the treatment of psoriasis, e.g., tapinarof, roflumilast, etc.). b) Any herbal or traditional medicines that could affect psoriasis efficacy evaluations (including but not limited to Chinese, Taiwanese, Korean, and other ethnic medicines).
 
4. Who did not complete the specified exposure to study agent as outlined below:
 
 Participants randomized to placebo who received guselkumab prior to Week 16 Participants randomized to guselkumab at Week 0 but did not receive all scheduled guselkumab administrations or received one or more placebo administrations prior to Week 16. 
Participants who discontinued the study agent due to unsatisfactory therapeutic effect or an adverse event (AE) of worsening of psoriasis, or participants who started prohibited medications and continued receiving study agents prior to the timepoint of per-protocol analysis will be included in the per-protocol analysis and ICE rules specified will apply.

Scalp Special Site Analysis Set (SSSAS)	All participants who were randomized with ss-IGA score ≥ 3 at baseline. This analysis set will be used for the efficacy analyses for the scalp special site.
Genital Special Site Analysis Set (GSSAS)	All participants who were randomized with sPGA-G score ≥ 3 at baseline. This analysis set will be used for the efficacy analyses for the genital special site.
Intertriginous Special Site Analysis Set (ISSAS)	All participants who were randomized with an (i)-IGA score ≥ 3 at baseline. This analysis set will be used for the efficacy analyses for the intertriginous special site.
Facial Special Site Analysis Set (FSSAS)	All participants who were randomized with f-IGA score ≥ 3 at baseline. This analysis set will be used for the efficacy analyses for the face special site.
Safety Analysis Set (SAS)	All participants who received at least 1 (complete or partial) administration of study intervention (i.e., the treated population).
Immunogenicity Analysis Set (IAS)	All participants who received at least 1 (complete or partial) administration of guselkumab and who had at least 1 sample obtained after their first administration of guselkumab

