5.4. Secondary Endpoint(s) Analysis

5.4.1. Major Secondary Endpoint(s)

There are 12 major secondary endpoints for this study and listed below:

To evaluate the additional efficacy of guselkumab vs placebo

1. Change from baseline in BSA affected at Week 16
2. Change from baseline in total Psoriasis Area Severity Index (PASI) score at Week 16
3. The proportion of participants who achieve an IGA score of cleared (0) at Week 16
4. The proportion of participants who achieve a PASI 90 response at Week 16
5. The proportion of participants who achieve a PASI 100 response at Week 16
6. The proportion of participants who achieve a scalp-specific IGA (ss-IGA) score of absence of disease (0) or very mild disease (1) at Week 16 among randomized participants with an ss-IGA score ≥ 3 at baseline.
7. The proportion of participants who achieve a static Physician's Global Assessment of Genitalia (sPGA-G) score of clear (0) or minimal (1) at Week 16 among randomized participants with an sPGA-G score ≥ 3 at baseline
8. The proportion of participants who achieve an intertriginous IGA (i-IGA) score of clear (0) or minimal (1) at Week 16 among randomized participants with an i-IGA score ≥ 3 at baseline
9. The proportion of participants who achieve a facial IGA (f-IGA) score of clear (0) or minimal (1) at Week 16 among randomized participants with an f-IGA score ≥ 3 at baseline
10. The change from baseline in Psoriasis Symptom and Sign Diary (PSSD) total symptom score at Week 16
11. The proportion of participants who achieve ≥ 4 -point reduction (improvement) from baseline in the Psoriasis Symptom and Sign Diary (PSSD) itch score at Week 16, among participants with baseline PSSD itch score ≥ 4 at baseline
12. The proportion of participants with PSSD individual symptom scale score = 0 at Week 16, among randomized participants with baseline PSSD > 0 at baseline. (Note: In this endpoint "individual symptom scale score = 0" is defined as "total symptom score = 0")

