5.4.2. Supportive Secondary Endpoint(s)

In addition to the primary and major secondary endpoints, other efficacy endpoints will also be analyzed.

This section outlines the definition and analyses of the other efficacy endpoints.

Other efficacy endpoints through Week 16 will be analyzed at Week 16 DBL and other efficacy endpoints through Week 48 will be analyzed at Final DBL.

5.4.2.1. Other efficacy endpoint through Week 16

1. Change from baseline in BSA \times IGA through Week 16.
2. Time to complete scalp psoriasis clearance (ss-IGA = 0) through week 16, among randomized participants with scalp psoriasis at baseline
3. Proportion of participants with complete scalp psoriasis clearance (ss-IGA = 0) over time among randomized participants with scalp psoriasis at baseline over time through Week 16.

4. Proportion of participants who achieve an ss-IGA score of absence of disease (0) or very mild disease (1) with at least 2-grade improvement from baseline at Week 16 among randomized participants with an ss-IGA score ≥ 2 at baseline.
5. Time to complete genital psoriasis clearance (sPGA-G = 0) through week 16, among randomized participants with genital psoriasis at baseline
6. Proportion of participants with complete genital psoriasis clearance (sPGA-G = 0) among randomized participants with genital psoriasis at baseline over time through Week 16.
7. Proportion of participants who achieve an sPGA-G score of clear (0) or minimal (1) with at least 2-grade improvement from baseline at Week 16 among randomized participants with an sPGA-G score ≥ 2 at baseline.
8. Time to complete intertriginous psoriasis clearance (i-IGA = 0) through week 16, among randomized participants with intertriginous psoriasis at baseline
9. Proportion of participants with complete intertriginous psoriasis clearance (i-IGA = 0) among randomized participants with intertriginous psoriasis at baseline over time through Week 16
10. Proportion of participants who achieve an i-IGA score of clear (0) or minimal (1) with at least 2-grade improvement from baseline at Week 16 among randomized participants with an i-IGA score ≥ 2 at baseline.
11. Time to complete facial psoriasis clearance (f-IGA = 0), through week 16, among randomized participants with facial psoriasis at baseline.
12. Proportion of participants with complete facial psoriasis clearance (f-IGA = 0) among randomized participants with facial psoriasis at baseline over time through Week 16.

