13. Proportion of participants who achieve an f-IGA score of clear (0) or minimal (1) with at least 2-grade improvement from baseline at Week 16 among randomized participants with an f-IGA score ≥ 2 at baseline.
14. The change from baseline in individual scale score of PSSD components at Week 16
15. The proportion of participants who achieve a PSSD individual scale score of 0 at Week 16 among randomized participants with scale score ≥ 1
16. The proportion of participants who achieve a PSSD symptom score = 0 at Week 16 among randomized participants with PSSD symptom score ≥ 1
17. The proportions of participants who achieve a PSSD symptom score = 0 and a PSSD sign score = 0 and the proportion of participants who achieve a PSSD individual scale score of 0 for participants with a baseline symptom score, sign score, and each PSSD individual baseline scale score that is ≥ 1 over time through Week 16
18. The proportion of participants with Dermatology Life Quality Index (DLQI) 0/1 at Week 16

19. The change from baseline in patient-reported outcomes measurement information system-29 (PROMIS-29) score over time through Week 16

5.4.2.2. Definition of other efficacy endpoint (s) through Week 16

Details refer to section [5.4.1.1.](#) and [5.4.2.5.](#)

5.4.2.3. Analysis method of other efficacy endpoint(s) through Week 16

Other efficacy endpoints through Week 16 will be tested regardless of the significance of the primary and major secondary endpoints; the testing of these endpoints will not be controlled for multiplicity. All statistical testing will be performed at the 2-sided 0.05 significance level. Nominal (unadjusted) p-values will be presented.

The analyses of these other efficacy endpoints through Week 16 will be based on FAS and special site analysis sets for the endpoints related to the special sites.

Descriptive statistics (i.e., N, mean, median, SD, IQ range, minimum, and maximum) will be used to summarize continuous variables. Counts and percentages will be used to summarize categorical variables. Graphical data displays (e.g., line plots) may also be used to summarize the data.

The comparisons of interest will be between guselkumab group and the placebo group.

The primary estimand approach and analysis methods specified for the primary endpoint in Sections [5.3.2.](#) and [5.3.3.](#), will apply to all continuous endpoints, binary endpoints, and time to event endpoints.

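### The SAP's special-site analysis sets (baseline score 3 or more) contradict the wording of the twelve Week 16 endpoints assigned to them

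*SAP*

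**What the plan says.** **The sets.** SAP Table 6 admits to the scalp set "All participants who were randomized with ss-IGA score" 3 or more at baseline, and to the genital set "All participants who were randomized with sPGA-G score" 3 or more. The intertriginous and facial sets follow the same rule on i-IGA and f-IGA. Their use is not confined to the major secondary endpoints. Of the scalp set the table says: "This analysis set will be used for the efficacy analyses for the scalp special site".

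**Where they are used.** SAP Section 5.4.2.3 says that the analyses of the other efficacy endpoints through Week 16 "will be based on FAS and special site analysis sets for the endpoints related to the special sites". The ss-IGA definition under Section 5.4.1.1 separately restates the limit of 3 or more for the ss-IGA analysis.

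**The endpoints so assigned.** Section 5.4.2.1 describes wider groups. Endpoint 4 asks for a scalp score of 0 or 1 "with at least 2-grade improvement from baseline at Week 16 among randomized participants with an ss-IGA score" of 2 or more; endpoints 7, 10 and 13 do the same for the other three sites. Endpoints 2 and 3 (time to scalp clearance, proportion cleared) are "among randomized participants with scalp psoriasis at baseline", with no severity threshold; endpoints 5, 6, 8, 9, 11 and 12 match them for the other sites.

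**The neighbouring confirmatory endpoints.** Major secondary endpoint 6 is "The proportion of participants who achieve a scalp-specific IGA (ss-IGA) score of absence of disease (0) or very mild disease (1) at Week 16" in those with a baseline score of 3 or more. Endpoints 7 to 9 are its counterparts for genital, intertriginous and facial disease.

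**The protocol.** Table 3 of the protocol describes the scalp set as "All participants who were randomized in the study within scalp special site involvement at baseline". It gives no score.

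**The concern.** The only thing the 2-grade rule adds to a plain 0/1 response is how it treats someone who starts at 2 and ends at 1. A set that begins at 3 contains no such person, so the four 2-grade endpoints would repeat results already reported as major secondary endpoints 6 to 9 and look like extra evidence.

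The clearance endpoints would describe moderate or worse site disease under a label that says all site psoriasis. Milder disease at a second site can occur, because inclusion criterion 3 asks for a score of 3 or more at only one site.

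These twelve are items 2 to 13 of the 19 other Week 16 endpoints in Section 5.4.2.1, in a trial whose subject is special-site disease. If the conflict is left in place, someone must choose the population while programming, possibly after the Week 16 unblinding.

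**Working it through.** **Step 1. The plan's own per-site figure.** SAP Table 4 gives 90% power with 25 placebo and 50 guselkumab participants per site, 2-sided alpha 0.05. The normal approximation with pooled variance under the null is

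power = Φ{[Δ − 1.96·√(p̄(1−p̄)(1/25+1/50))] / √(p₀(1−p₀)/25 + p₁(1−p₁)/50)}.

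For scalp, p₀ = 0.15, p₁ = 0.52 and p̄ = (25×0.15 + 50×0.52)/75 = 0.3967. The null standard error is √(0.3967×0.6033×0.06) = 0.1198. The alternative standard error is √(0.0051 + 0.004992) = 0.1005. Then (0.37 − 1.96×0.1198)/0.1005 ≈ 1.345, and Φ = 0.9107.

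| Site | Placebo | Guselkumab | Power |
|---|---|---|---|
| Scalp | 15% | 52% | 0.9107 |
| Genital | 10% | 45% | 0.9095 |
| Intertriginous | 10% | 45% | 0.9095 |
| Face | 25% | 63% | 0.8978 |

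The stated 90% is reproduced. It concerns endpoints defined on 3 or more, so the conflict does not touch it.

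**Step 2. Set against endpoint.**

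| Endpoints | Baseline group in the endpoint wording | Set assigned | Both applied together |
|---|---|---|---|
| Major secondary 6–9 | 3 or more | 3 or more | 3 or more |
| Other 4, 7, 10, 13 | 2 or more | 3 or more | 3 or more |
| Other 2, 3, 5, 6, 8, 9, 11, 12 | any site psoriasis | 3 or more | 3 or more |

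Keeping the endpoint wording as a filter inside the named set does not help, because the narrower condition wins. The worded population is reached only by disregarding the named set.

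**Step 3. Does the 2-grade rule change any classification?** Compare response A (Week 16 score of 0 or 1) with response B (A plus a fall of at least 2 grades) over every pair of baseline and Week 16 scores.

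| Scale | Baseline | Pairs | Pairs where A and B differ |
|---|---|---|---|
| ss-IGA, i-IGA, f-IGA (0–4) | 3 or more | 2×5 = 10 | 0 |
| sPGA-G (0–5) | 3 or more | 3×6 = 18 | 0 |
| ss-IGA, i-IGA, f-IGA (0–4) | 2 or more | 3×5 = 15 | 1 (2 to 1) |
| sPGA-G (0–5) | 2 or more | 4×6 = 24 | 1 (2 to 1) |

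The smallest fall from 3 or more to 0 or 1 is 3 − 1 = 2, so A and B coincide.

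**Step 4. Do the other rules match?** In both families, the first two intercurrent events count as non-response, observed values are used after the third, and missing Week 16 data count as non-response (SAP Sections 5.4.1.3.2 and 5.4.2.3, the latter through Sections 5.3.2 and 5.3.3). Numerators and denominators are therefore the same. Only the p-value could differ, because Section 5.4.2.3 leaves the choice between chi-square and CMH open.

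**Step 5. How many participants?** The documents do not say. As an illustration only, suppose 75 participants score 3 or more at a site and a share m of those scoring 2 or more score exactly 2. The number left out of that site's 2-grade endpoint is 75m/(1−m): about 8 for m = 10%, 25 for m = 25% and 75 for m = 50%. Both inputs are assumptions. The 75 is the enrolment target for a stratum, and the Table 6 sets also take in anyone scoring 3 or more at that site who was randomised under another.

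**The case against.** The strongest reply is that nothing has been lost yet. The SAP kept each endpoint's own baseline condition, and its Appendix 2 lists psoriasis at each site separately from the site as randomised. A programmer could follow the endpoint wording and produce what was meant. This stands to the extent that the duplication and the exclusions are conditional on the named sets governing. It does not remove the contradiction: Table 6, Section 5.4.2.3 and, for scalp, the ss-IGA definition all point to 3 or more.

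A reader might infer that the protocol already defines the sets as a score of 1 or more in any stratum, and that the SAP departs from it. The protocol sets no threshold, and its phrase about being randomised within site involvement could also mean the randomisation stratum.

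A reader might also take SAP Table 9, which adds the cut-off of 3 to the set names, as proof that a wider set was intended. It is suggestive only. The SAP restates conditions elsewhere, for example giving the baseline qualifier twice in major secondary endpoint 11.

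It is fair, too, that all twelve endpoints lie outside the testing hierarchy.

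**Conclusion.** The SAP contradicts itself on the population for twelve Week 16 special-site endpoints. If the named sets govern, all four 2-grade endpoints have the same participants and the same responders as major secondary endpoints 6 to 9, and all eight clearance endpoints exclude participants scoring 1 or 2 at that site. The first result is a matter of logic and needs no assumption about response rates. The second takes effect only if such participants are enrolled, which eligibility allows.

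Two stronger conclusions are tempting. One is that a large part of the sample is discarded. The documents give no count of milder site disease, and a figure pooling scores 1 and 2 would not apply to the 2-grade endpoints in any case. Those left out of a site analysis also remain in the Full Analysis Set. The other is that confirmatory results are at risk. The primary endpoint, major secondary endpoints 6 to 9 and the Table 4 power are unaffected, and the twelve endpoints carry nominal p-values. The point should be corrected, but it does not threaten the trial's main conclusion.

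**What to change.** Amend the SAP before the Week 16 database lock, consistent with protocol Section 9.4, which has it final before the first lock and unblinding:

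- In Table 6, define the four site sets by involvement at baseline. State that this means a site score of 1 or more, regardless of randomisation stratum. This settles a point the protocol leaves open and should be presented as such.
- In Sections 5.4.1 and 5.4.2, give the baseline filter endpoint by endpoint: 3 or more for major secondary endpoints 6 to 9, 2 or more for other endpoints 4, 7, 10 and 13, and any involvement for clearance and time to clearance.
- Amend the ss-IGA definition under Section 5.4.1.1, so that the limit of 3 applies only to major secondary endpoint 6. Changing Table 6 alone would leave the scalp conflict in place.

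The cost is SAP wording and subset flags in the analysis data. The Schedule of Activities lists every site score at baseline. Protocol Appendix 11 speaks of ss-IGA for participants with scalp psoriasis, and those are the participants the wider scalp set needs. Sample size, alpha and the testing order do not change.

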5. STATISTICAL ANALYSES

5.1. General Considerations

In general, descriptive statistics will include counts and percentages for categorical variables, and mean, standard deviation (SD), median, interquartile (IQ) range, minimum, and maximum for continuous variables. Graphical data displays may also be used to summarize the data.

In this study, efficacy will be evaluated through Week 48. In addition, PK, immunogenicity, PD, biomarker, and safety measurement, and selected participant information data will be collected through Week 56.

Analyses and summaries (including overtime summaries) in general will be carried out during the following study periods when appropriate:

1. From Week 0 through Week 16 (Placebo Controlled Period)
2. From Week 0 through Week 48 (Placebo Controlled and Active Treatment Period)
3. From Week 0 through Week 56

Binary Response Efficacy Endpoints

For binary response efficacy endpoints, treatment comparisons will generally be performed using a Cochran-Mantel-Haenszel (CMH) test stratified by special site (scalp, face, intertriginous, and genital) involvement. The magnitude of the treatment difference will be estimated by the difference in response rates between the guselkumab and placebo groups with a 95% confidence interval (CI) calculated based on Wald statistics (Kim and Won, 2013).

For special site related binary response efficacy endpoints, treatment comparisons will generally be performed using a Chi-squared test. The magnitude of the treatment difference will be estimated by the difference in response rates between the guselkumab and placebo groups with a 95% confidence interval (CI) calculated.

In case of rare events the Fisher's exact test will be used for treatment comparisons as appropriate. The proportion difference between guselkumab group and placebo and the exact confidence interval will be calculated. In these analyses, participants with missing data will be imputed as not achieving the response.

Continuous Efficacy Endpoints

For continuous efficacy endpoints, treatment comparisons will be performed using a Mixed Effects Model for Repeated Measures (MMRM), which relies on the Missing at Random (MAR) assumption for the missing responses. Under the assumption of MAR, the missing data will be accounted for through correlation of repeated measures in the model.

The explanatory variables of the MMRM model will include treatment group, visit, baseline efficacy endpoint score, special site (scalp, face, intertriginous, and genital) an interaction term of visit with treatment group, and an interaction term of visit with baseline efficacy endpoint score. An unrestricted (UN) variance-covariance matrix for repeated measures within a participant will be used. If the model with unstructured covariance structure does not converge, alternative covariance structures will be tried in the following order, with the first structure that converges being used in the analysis: heterogeneous Toeplitz (TOEPH) or autoregressive of order 1 (AR (1)).

The baseline measurement is defined as the closest measurement taken prior to or at the time of the first study agent administration date unless otherwise specified.

The change from baseline is calculated as the post baseline value minus the baseline value.

Change from baseline= Post Baseline Value – Baseline Value

Percent Change from Baseline= ((Post Baseline Value-Baseline Value)/Baseline Value) *100

If a higher score indicates more severe disease in efficacy assessments, then a negative change indicates an improvement, and a positive change indicates worsening.

The treatment difference between a guselkumab group and the placebo group will be estimated by the difference in the LS means. The 95% CIs for the differences in LS means and p-values will be calculated.

Time to an Event Efficacy Endpoints

Survival analysis techniques such as life-table estimates will be calculated for time to event efficacy endpoints for the 2 treatment groups. The log-rank test stratified by special site (scalp, face, intertriginous, and genital) will be used to compare the time to event efficacy endpoints. For the special site related endpoints, stratification will not be used for the log rank test to compare the time to event efficacy endpoints.

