5.3.4. Subgroup Analyses

The consistency of treatment effect, the primary endpoint will be evaluated for the subgroups defined in Section 5.7.8, using the primary estimand (**Estimand 1**). For each subgroup analysis, the analysis set is the individual subgroup (Section 5.7.8) of the primary efficacy analysis set.

- For each of the subgroups, the difference between the guselkumab treatment group and placebo group in the proportion of participants achieving IGA score of cleared (0) or

minimal (1) at Week 16 and its 95% confidence interval (when the numbers of participants permit) will be calculated.

In addition, the primary endpoint at Week 16 by region, country and investigator site will be summarized.

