5.3.5. Summary of Analyses Related to the Primary Endpoint

Table 7 below provides an overview of the analyses related to the primary endpoints, the estimands, the analysis sets, the data handling rules to be used, and the analysis methods and summary statistics.

Table 7: Summary of Analyses Related to the Primary Endpoint at Week 16

Analysis (Analysis Set)	Missing data	Analysis method/Summary statistics
Analyses based on Primary Estimand (Estimand 1) , where ICEs 1-2 are handled by the composite strategy , and ICE 3 is handled by the treatment policy strategy		
Full Analysis Set (FAS)	Missing data due to missed visits or missed data collection. Participants with missing data are considered to be non-responders' imputation (NRI)	
 Summaries of the proportion of participants who achieved the endpoint Treatment difference (guselkumab group-placebo group) and 95% CI P-values based on CMH chi-squared test stratified by special site and represent the comparison with placebo.
Subgroup Analyses (Individual subgroup levels defined in Section 5.7.8, Full Analysis Set (FAS))	Missing data due to missed visits or missed data collection. Participants with missing data are considered to be non-responders' imputation (NRI)	
 Summaries of the proportion of participants who achieved the endpoint by subgroup Treatment difference (guselkumab group-placebo group) and 95% CI P-values based on CMH chi-squared test stratified by special site and represent the comparison with placebo.
Analyses based on Supplementary Estimand (Estimand 2) , where all the intercurrent events are addressed by the composite strategy in which non-responder is used after the occurrence of an ICE.		
Supplementary Analysis 1 (Full Analysis Set (FAS))	Missing data due to missed visits or missed data collection. Participants with missing data are considered to be non-responders' imputation (NRI)	
 Summaries of the proportion of participants who achieved the endpoint Treatment difference (guselkumab group-placebo group) and 95% CI P-values based on CMH chi-squared test stratified by special site and represent the comparison with placebo.

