5.7.6. Health Economics

No health economics measurement is collected in this study.

5.7.7. Other Variables and/or Parameters**5.7.7.1. Definition****5.7.7.2. Analysis Method****5.7.8. Definition of Subgroups**

To evaluate the consistency of efficacy based on demographic characteristics, baseline disease characteristics, and psoriasis medication history, subgroup analyses will be performed for the primary endpoint and selected major secondary endpoints. The subgroups for subgroup analyses include, but are not limited to, the following:

Baseline demographics

- Sex (male, female)
- Race/ethnicity (White, Black, Asian, Hispanic or Latino, Multi-Racial, Middle Eastern, American Indian/Indigenous/Alaskan Native, Pacific Islander/Native Hawaiian, Other)
- Geographic location ((United States, Canada)
- Baseline Age (≤ 30 , >30 to ≤ 45 , >45)
- Baseline weight (≤ 90 kg, >90 kg)
- Baseline weight by quartiles
- BMI (Normal [<25], Overweight [25 to <30], Obese [≥ 30])

Baseline disease characteristics:

- Age at diagnosis (years) (<25 , ≥ 25)
- Psoriasis disease duration (years) (≤ 2 , >2 to ≤ 5 , >5)
- Psoriatic arthritis (3 groups: Yes Rheumatologist confirmed; PEST positive at screening, PEST negative at screening)
- Special site as randomized (Scalp, Face, Intertriginous, Genital)
- Additional special site (, Palmoplantar, Nail)
- Baseline DLQI (<10 , ≥ 10)
- Baseline PASI (<10 , ≥ 10 to <15 , ≥ 15)
- Baseline BSA (≥ 2 to <5 , ≥ 5 to <10 , ≥ 10 to ≤ 15)

Psoriasis medication history:

- Phototherapy (ultraviolet B light [UVB] or psoralen and ultraviolet A light therapy [PUVA])
 - ☐ Never used
 - ☐ Ever used
- Conventional systemics (PUVA, MTX, cyclosporine, acitretin)

-
- ☐ Never used
 - ☐ Ever Used
 - Advanced Orals (apremilast, deucravacitinib,)
 - ☐ Never used
 - ☐ Ever used
 - Topicals
 - ☐ Never used
 - ☐ Ever used
 - Participants who had an inadequate response to or intolerance to any of the following phototherapy: Ultraviolet B light [UVB] or psoralen and ultraviolet A light therapy [PUVA]
 - Yes
 - No
 - Participants who had an inadequate response to, or intolerance to any of the conventional systemic therapies (PUVA, MTX, acitretin or cyclosporine)
 - Yes
 - No
 - Participants who had an inadequate response to or intolerance to any of the conventional systemics, phototherapy, or apremilast
 - Yes
 - No
 - Participants who had an inadequate response to or intolerance to any of the advanced oral systemic therapies (apremilast, deucravacitinib,)

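### The only interval method the SAP names for a binary difference is Wald; read with site stratification into subgroups that span sites, it covers about 92% at n = 75 and about 86% at an assumed n = 30

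*SAP*

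**What the plan says.** SAP 5.1 sets the general rule for binary efficacy endpoints. The test is a "Cochran-Mantel-Haenszel (CMH) test stratified by special site (scalp, face, intertriginous, and genital) involvement", and the difference comes "with a 95% confidence interval (CI) calculated based on Wald statistics (Kim and Won, 2013". The cited reference deals with adjusted differences in stratified trials. The SAP itself writes out no weights, no variance formula and no rule for a site with nobody in one arm. SAP 5.4.1.3.1 repeats the pairing of stratified CMH and Wald for five binary secondary estimands.

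For subgroups, SAP 5.3.4 asks for the difference in IGA 0/1 "at Week 16 and its 95% confidence interval (when the numbers of participants permit) will be calculated". It names neither Wald nor stratification. The subgroup row of Table 7 (SAP 5.3.5) asks for the difference, a 95% interval and "P-values based on CMH chi-squared test stratified by special site and represent the comparison with placebo".

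The subgroup list in SAP 5.7.8 includes "Baseline weight by quartiles", nine race/ethnicity levels, and special site as randomized. It applies to the primary endpoint and to selected major secondary endpoints.

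For rare events, SAP 5.1 switches to Fisher's test: "The proportion difference between guselkumab group and placebo and the exact confidence interval will be calculated". It does not define rare.

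**The concern.** A stratified Wald interval estimates a variance inside each site and arm by plugging in the observed proportion. With few participants per cell, that estimate is biased low. It is exactly zero when everyone, or no one, in the cell responds. Splitting a modest subgroup four ways creates such cells.

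The subgroup analyses exist to judge consistency of effect. Intervals that are too short make chance differences between subgroups look more real than they are, most of all in the smallest subgroups.

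**Working it through.** **Inputs.** SAP section 3 gives 60% vs 15%, 200 vs 100 participants, a two-sided alpha of 0.05, and 50 vs 25 per special site. The four strata come from SAP 5.1. A weight quartile has 300/4 = 75 participants; I assume they are spread about evenly over the sites. No document gives a subgroup of 30; that size is an assumption. Protocol 4.1 aims for at least about 20% non-White participants. At exactly that floor this is 60 people over eight levels, or 7.5 on average, so levels of 30 or fewer are plausible.

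**The plan's own figures.** The plan states no coverage, so I reproduce its power. With pooled proportion (2 × 0.60 + 0.15)/3 = 0.45, SE under the null is √(0.45 × 0.55 × (1/200 + 1/100)) = 0.0609. Under the alternative it is √(0.24/200 + 0.1275/100) = 0.0497. Then (0.45 − 1.96 × 0.0609)/0.0497 = 6.64, so power exceeds 99.99%, which agrees with Table 3. The same method gives 91.1%, 90.9% and 89.8% for the special-site rates of Table 4 (90% stated). The inputs are therefore read correctly.

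**Why the interval is short.** The plug-in variance has expectation p(1−p)/n × (n−1)/n. Take equal strata and let n be the size of one arm within one site.

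- n = 75 over four sites (12.5 and 6.25 per cell): true variance 0.24/50 + 0.1275/25 = 0.00990. Expected plug-in: 0.0048 × 11.5/12.5 + 0.0051 × 5.25/6.25 = 0.00870. Width 2 × 1.96 × √0.00870 = 0.366, against 0.390 needed.
- n = 30 over four sites (5 and 2.5 per cell): true variance 0.24/20 + 0.1275/10 = 0.02475. Plug-in: 0.0120 × 4/5 + 0.01275 × 1.5/2.5 = 0.01725. Width 0.515, against 0.617.
- One site, 50 vs 25, one stratum: plug-in 0.0048 × 49/50 + 0.0051 × 24/25 = 0.00960. Width 0.384, against 0.390.

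So at n = 75 most of the shortfall comes from the stratification, not from the sample size.

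Zero variances are common. With six placebo participants in a site, the chance of no responder is 0.85^6 = 0.38. With three, the chance of all or none responding is 0.85³ + 0.15³ = 0.62. If ten placebo participants fall at random over four sites, some site has none with probability 4(0.75)^10 − 6(0.5)^10 + 4(0.25)^10 = 0.22. Under Mantel-Haenszel weights that site then drops out of the estimate.

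**Coverage.** Simulation used 200,000 replicates per scenario, Mantel-Haenszel weights and 60% vs 15%. Ranges run over near-equal and random site and arm sizes. The single-site row is exact enumeration.

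| Setting | Wald, plug-in | Wald, n−1 | Sato | Newcombe-type |
|---|---|---|---|---|
| N = 300, four strata | 94.4% | – | – | 94.9-95.0% |
| n = 75, four strata | 91.9-92.3% | 93.7-93.9% | 93.3-93.5% | 94.9% |
| n = 30, four strata | 84.7-87.2% | 89.3-91.6% | 89.8-91.6% | 94.9-95.0% |
| One site, 50 vs 25 | 93.6% | – | – | 94.7% |

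The last column is stratified except in the single-site row. Unstratified Newcombe covers 94.7-95.6% at n = 75, 60 and 30.

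Simulated mean plug-in widths against those needed are 0.364 vs 0.390 and 0.373 vs 0.404 at n = 75, which is 7-8% short. At n = 30 they are 0.508 vs 0.620 and 0.530 vs 0.679, which is 18-22% short.

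**Sensitivity.** The site-specific rates of Table 4 give 92.1-92.4% at n = 75 and 85.2-87.5% at n = 30. Rates near those reported in Protocol 2.2 for the earlier Phase 3 trials (85% vs 7%) give 90.0-90.6% and 80.4-86.6%. There the stratified Newcombe-type interval gives about 94.6% and 93.6%.

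**The case against.** Four points deserve weight.

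1. **The SAP never states a stratified Wald interval for subgroups.** Section 5.3.4 names no method, and in Table 7 the stratification wording qualifies the p-value. This stands as a matter of text. But Wald is the only method named outside the rare-event case, and its source is about stratified differences, so a programmer would most likely use it.
2. **There are safeguards.** The proviso in 5.3.4 could suppress intervals in very small subgroups, and an exact interval exists for rare events. Neither has a threshold. A quartile of 75 would hardly be suppressed, and 60% vs 15% is not rare.
3. **The size depends on a formula the SAP leaves to its reference.** This stands. A Sato or n-1 variance removes much of the loss at n = 75 but leaves a clear one at n = 30.
4. **Nothing rests on these intervals.** Subgroup results lie outside the testing sequence and carry no decision rule. For an estimate near 45 points, both the Wald and the wider interval exclude zero easily. This stands and limits the weight of the point.

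A reader might also infer that every subgroup is affected, or that the intervals are far too narrow. The documents support neither. Special site as randomized is a single stratum, so the mechanism cannot operate there, and a 7-8% shortfall at n = 75 is moderate.

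**Conclusion.** The point holds, at moderate size. Read naturally, the plan yields nominal 95% intervals that miss the true difference about 8 times in 100 in a weight quartile, and about 14 times in 100 in a subgroup of 30, instead of 5. With a Sato or n-1 variance the figures are about 6-7 and 8-11.

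This assumes the planning rates, 2:1 allocation, Mantel-Haenszel weights and subgroups spread over all four sites. The figure at 75 rests on a size that follows from the plan; the figure at 30 rests on an assumed size.

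It would be wrong to infer that the primary result is in doubt: its interval covers about 94.4%. Nor do the documents show that the four special-site endpoints need a different interval. No method is named for them, but unstratified Wald at 50 vs 25 and the rates of Table 4 covers 93.6-94.2%.

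**What to change.** In SAP 5.3.4 and the subgroup row of Table 7, name a score-type interval for subgroup differences, in one of two consistent forms:

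- stratified Newcombe or stratified Miettinen-Nurminen, beside the site-stratified CMH p-value; or
- unstratified Newcombe or Miettinen-Nurminen, with the subgroup p-value also unstratified.

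The coverage figures above were obtained for Newcombe-type intervals; Miettinen-Nurminen was not simulated.

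Replace the open proviso with a minimum subgroup size for reporting an interval. If stratification stays, say what happens when a site has no participant in one arm, and drop it for special site as randomized. Naming a method for the four special-site endpoints in 5.1 and 5.4.1.3.1 is optional.

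The cost is SAP wording and somewhat wider intervals. For stratified Newcombe-type against plug-in Wald, mean width with near-equal strata is 0.38 against 0.36 at n = 75, and 0.58 against 0.51 at n = 30. With random strata it is 0.39 against 0.37, and 0.62 against 0.53.
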